3.5.4. Vital Signs

Supine blood pressure (BP), pulse rate (PR) and temperature will be measured at times specified in the SoA given in the protocol.

For all periods, the baseline measurement is the predose measurement on Day 1 in each period. Changes from baseline will be defined as the change between the postdose and baseline measurements.

3.5.5. Electrocardiograms

QT interval, QTcF, PR interval, QRS and heart rate (HR) will be recorded at each 12-lead ECG assessment time indicated in the SoA given in the protocol. QTcF will be derived using Fridericia's heart rate correction formula:

 $QTcF = QT / (RR)^{(1/3)}$ where RR = 60/HR (if not provided)

For all periods, the baseline value is the average of triplicate ECG measurements collected predose on Day 1 of each period. Changes from baseline will be defined as the change between the postdose measurements and baseline value.

4. ANALYSIS SETS (POPULATIONS FOR ANALYSIS)

Data for all participants will be assessed to determine if participants meet the criteria for inclusion in each analysis population prior to releasing the database and classifications will be documented per standard operating procedures.

Participant Analysis Set	Description
Safety Analysis Set	All participants who take at least 1 dose of study intervention. Participants will be analyzed according to the product they actually received.
PK Concentration Set	All participants who take at least 1 dose of study intervention and in whom at least 1 concentration value is reported.
PK Parameter Set	All participants who take at least 1 dose of study intervention and in whom at least 1 of the PK parameters of interest are reported.

5. GENERAL METHODOLOGY AND CONVENTIONS

Final analysis will be performed after study participant data set release following last participant last visit.

5.1. Hypotheses and Decision Rules

No statistical hypothesis will be tested in this study.

5.2. General Methods

5.2.1. Analyses for Binary/Categorical Endpoints

For binary or categorical variables, number of participants, numbers and percentages of participants meeting the categorical criteria will be presented in accordance with the Clinical Data Interchange Standards Consortium and Pfizer Standards (CaPS).

5.2.2. Analyses for Continuous Endpoints

For continuous variables, the data will be summarized using the number of participants, mean, median, standard deviation (SD), minimum, and maximum in accordance with the CaPS. For appropriate PK parameters, geometric mean and geometric coefficient of variation (%CV) will also be summarized.

5.3. Methods to Manage Missing Data

5.3.1. Pharmacokinetic Data

Methods to handle missing PK data are described below.

Concentrations Below the Limit of Quantification:

In all data presentations (except listings), concentrations below the limit of quantification (BLQ) will be set to zero. In listings, BLQ values will be reported as "<LLQ", where LLQ will be replaced with the value for the lower limit of quantification.

Deviations, Missing Concentrations and Anomalous Values:

In summary tables and plots of median profiles, statistics will be calculated having set concentrations to missing if one of the following cases is true:

- 1. A concentration has been collected as ND (ie, not done) or NS (ie, no sample).
- 2. A deviation in sampling time is of sufficient concern or a concentration has been flagged anomalous by the pharmacokineticist.

Note that summary statistics will not be presented at a particular time point if more than 50% of the data are missing.

An anomalous concentration value is one that, after verification of bioanalytical validity, is grossly inconsistent with other concentration data from the same individual or from other participants. For example, a BLQ concentration that is between quantifiable values from the same dose is considered as anomalous. Anomalous concentration values may be excluded from PK analysis at the discretion of the PK analyst.

PK Parameters:

Actual PK sampling times will be used in the derivation of PK parameters. If a PK parameter cannot be derived from a participant's concentration data, the parameter will be coded as NC

DMB02-GSOP-RF02 7.0 Statistical Analysis Plan Template 31-Jan-2022 PFIZER CONFIDENTIAL TMF Doc ID: 98.03 Page 11 of 20 (ie, not calculated). (Note that NC values will not be generated beyond the day that a participant discontinues).

In summary tables, statistics will not be presented for a particular treatment group if more than 50% of the data are NC. For statistical analyses, PK parameters coded as NC will also be set to missing, and statistics will be presented for a particular treatment with \geq 3 evaluable measurements.

If an individual participant has a known biased estimate of a PK parameter (due for example to a dosing error or an unexpected event such as vomiting before all the compound is adequately absorbed from the gastrointestinal tract), this will be footnoted in summary tables and will not be included in the calculation of summary statistics or statistical analyses. For instance, if a participant has a vomiting event post dose that is within a duration of time that is 2-times the derived median T_{max} for the population for the administered treatment, then the pharmacokineticist should consider the exclusion of the PK concentration data collected following the initial vomiting event in that treatment period and the PK parameter data reported for that treatment period from the datasets used to calculate summary statistics or statistical analyses.

5.3.2. Safety Data

Missing values in standard summaries of safety data will be imputed according to CaPS.

6. ANALYSES AND SUMMARIES

6.1. Primary Endpoints

Plasma AUC_{last}, AUC_{inf} and C_{max} of etrasimod will be summarized by treatment group and will include the set of summary statistics as specified in Table 4.

For the evaluation of relative bioavailability of etrasimod 2 mg mini tablets mixed with applesauce, chocolate pudding and water compared to etrasimod 2 mg clinical IR tablets, *natural log transformed AUC_{inf}, AUC_{last} and C_{max} will be analyzed using a mixed effect model with sequence, period and treatment as fixed effects and participant within the sequence as a random effect. Estimates of the adjusted mean differences (Test Reference) and corresponding 90% CIs will be obtained from the model. The adjusted mean differences and 90% CIs for the differences will be exponentiated to provide estimates of the ratio of adjusted geometric means (Test/Reference) and 90% CI for the ratios. Treatment A (etrasimod 2 mg clinical IR tablets under fasted conditions) will be the Reference treatment while Treatment B (etrasimod 2 mg mini tablets mixed with applesauce under fasted conditions), and Treatment D (etrasimod 2 mg mini tablets mixed with water under fasted conditions) will be the Test treatments.*

For the evaluation of relative bioavailability of etrasimod 2 mg mini tablets mixed with yogurt compared to etrasimod 2 mg clinical IR tablets, *natural log transformed AUC*_{inf}, AUC_{last} and C_{max} will be analyzed using a mixed effect model with sequence and treatment as fixed effects and participant within the sequence as a random effect. Treatment A (etrasimod

DMB02-GSOP-RF02 7.0 Statistical Analysis Plan Template 31-Jan-2022 PFIZER CONFIDENTIAL TMF Doc ID: 98.03 Page 12 of 20 2 mg clinical IR tablets under fasted conditions) will be the Reference treatment while Treatment E (etrasimod 2 mg mini tablets mixed with yogurt under fasted conditions) will be the Test treatment.

For AUC_{inf}, AUC_{last} and C_{max} , a listing of the individual participant ratios (Test/Reference) will be provided. Box and whisker plots for AUC_{inf}, AUC_{last} and C_{max}, will be plotted by treatment and overlaid with geometric means.

Residuals from the models will be examined for normality and the presence of outliers via visual inspection of plots of residuals vs predicted values and normal probability plots of residuals but these will not be included in the CSR. If there are major deviations from normality or outliers then the effect of these on the conclusions will be investigated through alternative transformations and/or analyses excluding outliers. Justification for any alternative to the planned analysis will be given in the report of the study.

6.2. Secondary Endpoints

6.2.1. Safety data

Analyses and summaries of safety data are described in Section 6.6.

6.2.2. Palatability of etrasimod mini tablets

The sensory attributes (mouth feel, bitterness, sweetness, sourness, saltiness, tongue/mouth burn, overall liking) from the Taste Assessment Questionnaire will be listed and descriptively summarized by treatment, and question across participants. Summary statistics (mean and 90% CI) will be calculated for the various questions. Radar plots for each of 4 time points (1, 5, 10 and 20 minutes after dosing), summarizing all attributes for each treatment will be generated.

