#### 8.10. Palatability Assessments

Palatability assessment of the etrasimod mini tablets will be conducted in every period for Treatments B, C, D, E with the aid of a questionnaire (Appendix 9). The palatability assessment questionnaire will be administered to participants by trained staff using a colored copy of the questionnaire. After study intervention administration, participants will be asked to rate the mouth feel, bitterness, tongue/mouth burn, throat burn, and overall liking. The participants will rate the above within 1 minute (immediately) after dosing, before drinking water that is given as part of dosing, and at 5 minutes, 10 minutes, 20 minutes after dosing is fully completed.

See Appendix 9 for the details about the palatability assessment questionnaire.

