# 9.3.4. Palatability Assessment Analyses

The data used in the palatability assessment analysis will be transcribed and rescaled to a score from 0 to 100 from the raw measurements on the palatability questionnaire. The sensory attributes (mouth feel, bitterness, tongue/mouth burn, throat burn, and overall liking) from the palatability assessment questionnaire (Appendix 9) for each treatment will be listed and descriptively summarized by collection time. Radar plots for each time point, summarizing all attributes, will be generated.

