### **Background information**

Study #/Study Site	
Period and Day	
Participant ID (Rand ID)	
Treatment	
Collection Date	
Collected by	
Entered in PIMS by	
Checked in PIMS by	
Questionnaire Fully Completed (circle one)	Yes/No

Please answer the following questions and provide a mark  $(\times)$  on the color bar at 1 (immediately), 5, 10 and 20 minutes after dosing. Please ensure participant has access to these descriptions when completing the questionnaire.

Q1: Mouth feel – Please tell us about the mouth feel (such as grittiness, stickiness, waxiness) of the product you tasted.

Q2: Bitterness – Please tell us about the degree of bitterness of the product you tasted.

Q3: Tongue/mouth burn – Please tell us about the degree of tongue/mouth burn of the product you tasted.

Q4: Throat burn – Please tell us about the degree of throat burn of the product you tasted.

Q5: Overall liking – Please indicate how much you like or dislike the product you tasted.

Good (score = 0)

Example: How to provide a mark (×) on the color bar.

Х

Bad (score = 100)

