# Provide a mark ( × ) on the color bar **Mouth Feel Tongue/Mouth Overall Liking** Bitterness **Throat Burn** Burn Good Bad

**Collection time:** 

# 20 minutes after dosing Collection time: Provide a mark ( × ) on the color bar

	Mouth Feel	Bitterness	Tongue/Mouth Burn	Throat Burn	Overall Liking
G					
B	ad 🛛				

**Additional feedback** – After completing the "20 minute after dosing" palatability questions, please provide any additional descriptive feedback in the box below regarding the taste or odor of the product.

PFIZER CONFIDENTIAL CT02-GSOP Clinical Pharmacology Protocol Template (14 April 2023) Page 97

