2.1. Modifications to the Analysis Plan Described in the Protocol

None.

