2.2. Study Objectives and Endpoints

Objectives	Endpoints
Primary:	Primary:
• To estimate the rBA of etrasimod 2 mg mini tablets mixed with water compared with etrasimod 2 mg clinical IR tablets under fasted conditions	• Plasma AUC _{lasb} AUC _{inf} and C _{max} of etrasimod
• To estimate the rBA of the etrasimod 2 mg mini tablets mixed with apple sauce compared with the etrasimod 2 mg clinical IR tablets under fasted conditions	

Objectives	Endpoints
• To estimate the rBA of the etrasimod 2 mg mini tablets mixed with chocolate pudding compared with the etrasimod 2 mg clinical IR tablets under fasted conditions	
• To estimate the rBA of the etrasimod 2 mg mini tablets mixed with yogurt compared with the etrasimod 2 mg clinical IR tablets under fasted conditions	
Secondary:	Secondary:
• To evaluate the safety and tolerability of etrasimod in healthy participants	• Assessment of first dose HR reduction, TEAEs, clinical laboratory abnormalities, vital signs, PEs, and 12-lead ECGs
• To assess the palatability of etrasimod mini tablets mixed with water/apple sauce/chocolate pudding/yogurt	• Assessment of palatability via questionnaire: mouth feel, bitterness, tongue/mouth burns, throat burn, and overall liking
Tertiary/Exploratory:	Tertiary/Exploratory:
• To characterize the PK parameters of etrasimod 2 mg mini tablets mixed with water or soft foods (apple sauce, chocolate pudding, or yogurt) compared with etrasimod 2 mg clinical IR tablet	• Plasma etrasimod: t _{1/2} , CL/F, V _z /F and T _{max} of etrasimod
• To validate the PK measurement of etrasimod in capillary blood sample collected using a micro sampling device against the PK measurement of etrasimod in venous blood samples.	• Plasma concentration of etrasimod obtained via micro sampling compared to venous sampling

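### SAP 6.2.2 lists the wrong palatability attributes: throat burn, which is collected, is left out, and sweetness, sourness and saltiness, which are not collected, are put in

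*SAP*

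**What the plan says.** SAP 6.2.2 sets out the palatability analysis as follows: "The sensory attributes (mouth feel, bitterness, sweetness, sourness, saltiness, tongue/mouth burn, overall liking) from the Taste Assessment Questionnaire will be listed". The sentence goes on to promise descriptive summaries by treatment and question. The section then adds means with 90% CIs, and radar plots of all attributes at 1, 5, 10 and 20 minutes.

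The rest of the plan gives a different list:

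- SAP 2.2 defines the secondary endpoint as "Assessment of palatability via questionnaire: mouth feel, bitterness, tongue/mouth burns, throat burn, and overall liking". Protocol Section 3 uses the same definition.
- Protocol 8.10 says that after dosing "participants will be asked to rate the mouth feel, bitterness, tongue/mouth burn, throat burn, and overall liking".
- Protocol 9.3.4 plans the analysis of "The sensory attributes (mouth feel, bitterness, tongue/mouth burn, throat burn, and overall liking) from the palatability assessment questionnaire (Appendix 9"), which "for each treatment will be listed and descriptively summarized by collection time".
- The questionnaire in Appendix 9 has five scored items. The fourth reads "Please tell us about the degree of throat burn of the product you tasted". After the 20-minute scores the only other response is a free-text box: "please provide any additional descriptive feedback in the box below regarding the taste or odor of the product".

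SAP 2.1, headed "Modifications to the Analysis Plan Described in the Protocol", contains the single word None.

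**The concern.** The SAP section that a programmer would work from does not match the endpoint that the same SAP defines, nor the form on which the data are recorded. A collected component of a secondary endpoint, throat burn, is missing from the list of attributes to be listed, summarized and plotted. Three attributes that participants are never asked to score are on that list.

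SAP 6.2.2 also names the instrument the Taste Assessment Questionnaire, a title found nowhere else in either document. SAP 3.2.2 and the protocol speak of a palatability questionnaire. That would fit text carried over from another study, but the documents do not give the cause.

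At stake is an incomplete report of a stated secondary objective, or an undeclared departure from the SAP if the list is silently corrected at programming.

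**Working it through.** The main check is a comparison of lists; no power or sample-size figure is involved.

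**Step 1. Lists side by side**

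| Attribute | Appendix 9 scored item | Protocol 3, 8.10, 9.3.4 and SAP 2.2 | SAP 6.2.2 |
|---|---|---|---|
| Mouth feel | yes | yes | yes |
| Bitterness | yes | yes | yes |
| Tongue/mouth burn | yes | yes | yes |
| Throat burn | yes | yes | **no** |
| Overall liking | yes | yes | yes |
| Sweetness | no | no | **yes** |
| Sourness | no | no | **yes** |
| Saltiness | no | no | **yes** |

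Four attributes agree, one collected attribute is omitted, and three listed attributes have no scored item. The free-text box cannot supply 0 to 100 scores for those three.

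**Step 2. Could something innocent explain it?**

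- *Version difference.* SAP version 1 (25 May 2023) is tied to the original protocol of 03 Apr 2023. The Amendment 1 summary of changes has no palatability entry, and SAP 2.2 already carries the correct five.
- *Deliberate modification.* Protocol Section 9 allows the SAP to modify the protocol analysis, but SAP 2.1 declares no modification. A change to the analysis plan also could not create data for items absent from the form.
- *Text lost from the PDF.* The color bars in Appendix 9 are not reproduced, but the five item texts and the column headings are intact.

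**Step 3. Size**

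Inputs: 4 mini-tablet treatments, B to E (protocol 8.10); 4 time points (SAP 6.2.2); 5 scored attributes (Appendix 9); 16 participants, of whom 12 evaluable are to complete (protocol 4.1).

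- Collected cells: 4 treatments × 4 times × 5 attributes = 80. Throat burn: 4 × 4 = 16, and 16/80 = 20%.
- Ratings with 16 participants: 16 × 80 = 1,280. Throat burn: 16 × 16 = 256.
- Ratings with 12 participants: 12 × 80 = 960. Throat burn: 12 × 16 = 192, again 20%.
- Cells in the SAP 6.2.2 grid: 4 × 4 × 7 = 112. Sweetness, sourness and saltiness: 3 × 16 = 48, and 48/112 = 43% with no data source.

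**Step 4. Collection time**

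Protocol 9.3.4 asks for listings and summaries by collection time. The corresponding sentence in SAP 6.2.2 gives treatment and question only; time appears there only for the radar plots.

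**The case against.** The best case for the plan is that throat burn is not truly without an analysis. Protocol 9.3.4 names it and plans its listing, its summary and its place on the radar plots. SAP 2.1 says that this plan is unchanged, SAP 2.2 names throat burn in the endpoint, and SAP 3.2.2 scores the questionnaire without leaving out any item. SAP 6.2.2 itself speaks generally of the various questions and of all attributes. On this reading one faulty parenthesis contradicts an otherwise sound plan. Programming would probably expose it, since three variables would not exist and one scored column would be unassigned.

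Much of that is fair as to consequence. The documents together still show what was meant, and nothing is lost at collection. The counts in Step 3 all restate one attribute in five. The 43% figure measures empty cells, not lost data. The 12-participant figures are only illustrative, because no rule limits palatability summaries to completers. The collection-time point is minor.

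It does not remove the error. The general phrases in 6.2.2 refer back to the list in the same paragraph, so they do not settle whether seven or five attributes are meant. Because the protocol lets the SAP modify its analyses, a reader cannot simply assume that the protocol list prevails.

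**Conclusion.** The error is real and clear from the text. SAP 6.2.2 omits 1 of the 5 collected attributes and lists 3 of 7 that are not collected. It contradicts the questionnaire, the protocol and the SAP's own endpoint definition, with no declared modification. Applied literally with 16 participants and complete questionnaires, it leaves 256 of 1,280 ratings (20%) outside the listed attributes.

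The practical weight is modest. The endpoint is secondary and descriptive, no hypothesis is tested, the throat-burn scores remain available, and the primary PK analysis is unaffected. It should be corrected, but it does not threaten the study. The only assumption is that Appendix 9 is the form in use, as protocol 8.10 and 9.3.4 both state.

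**What to change.** Replace the first sentence of SAP 6.2.2 so that it does three things:

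- names exactly the five scored attributes: mouth feel, bitterness, tongue/mouth burn, throat burn and overall liking;
- identifies the instrument as the Etrasimod Palatability Questionnaire in protocol Appendix 9, in place of the Taste Assessment Questionnaire;
- calls for listing and descriptive summary by treatment, question and collection time.

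The radar-plot sentence can stay, since all attributes will then mean those five. The cost is a one-sentence SAP correction, best made before database lock. The questionnaire, the data collection and the protocol need no change.

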6.3. Other Endpoints

6.3.1. Other PK parameters of etrasimod

Exploratory endpoints include other PK parameters of etrasimod such as T_{max} , $t_{1/2}$, CL/F and V_z /F. The PK parameters will be listed and summarized descriptively by treatment group in accordance with Pfizer data standards on the PK Parameter Set, as data permit. Missing values will be handled as detailed in Section 5.3.1. Each PK parameter will be summarized by treatment group and will include the set of summary statistics as specified in Table 4.

Parameter	Summary Statistics
AUC _{inf} , AUC _{last} , C _{max} ,	N, arithmetic mean, median, SD, %CV, minimum, maximum,
CL/F, V _z /F T _{max}	geometric mean and geometric %CV N, median, minimum, maximum
t _{1/2}	N, arithmetic mean, median, SD, %CV, minimum, maximum

 Table 4.
 PK Parameters to be Summarized Descriptively by Treatment

Supporting data from the estimation of $t_{/_2}$ and AUC_{inf} will be listed by analyte and group: terminal phase rate constant (k_{el}); goodness of fit statistic from the log-linear regression (r²); the percent of AUC_{inf} based on extrapolation (AUC_{extrap}%); and the first, last, and number of time points used in the estimation of k_{el}. This data may be included in the clinical study report.

PK Concentrations:

The plasma concentrations will be listed and descriptively summarized by nominal PK sampling time and treatment. Individual participant, as well as mean and median profiles of the plasma concentration-time data will be plotted by treatment using actual (for individual) and nominal (for mean and median) times respectively. Mean and median profiles will be presented on both linear and semi-log scales.

Presentations of concentrations will include:

- A listing of all concentrations sorted by participant ID, treatment and nominal time postdose. The concentration listing will also include the actual times. Deviations from the nominal time will be given in a separate listing.
- A summary of concentrations by treatment and nominal time postdose, where the set of statistics will include n, mean, median, SD, %CV, minimum, maximum and the number of concentrations above the LLQ.
- Median concentrations time plots (on both linear and semi-log scales) against nominal time postdose by treatment (all treatments on the same plot per scale, based on the summary of concentrations by treatment and time postdose).
- Mean concentrations time plots (on both linear and semi-log scales) against nominal time postdose by treatment (all treatments on the same plot per scale, based on the summary of concentrations by treatment and time postdose).
- Individual concentration-time plots by treatment (on both linear and semi-log scales) against actual time postdose (there will be separate spaghetti plots for each treatment per scale).
- Individual concentration-time plots by participant (on both linear and semi-log scales) against actual time postdose [there will be separate plots for each participant (containing all treatments) per scale].

